## 1 PROTOCOL SUMMARY

### 1.1 SYNOPSIS

Title:	Postpartum progestin-only pill use and breastfeeding study
Study Description:	This study will assess the impact of early initiation (less than one week postpartum) and delayed initiation (4 weeks postpartum) of two types of progestin-only contraceptive pills on maternal, breastmilk, and infant outcomes. This is a placebo-controlled randomized controlled trial enrolling dyads of mothers and their newborn babies. We will explore if the type and timing of initiation of pills is acceptable to the user with minimal side effects, impacts the supply or composition of breastmilk, and/or affects infant growth.
Aims:	Specific Aim: To determine whether the type of progestin used (drospirenone in drospirenone-containing progestin-only pills (d-POPs) vs. norethindrone in norethindrone-containing progestin-only pills (n-POPs)) or the timing of progestin initiation (early vs. delayed) affects: Aim 1a Maternal: the duration of exclusive breastfeeding continuation or the rates and types of breastfeeding supplementation over 8 weeks postpartum. Aim 1b Maternal: the proportion of mothers using progestin-only pills at 8 weeks postpartum. Aim 2 Milk: the composition of breastmilk (fat, protein, carbohydrates) at 4 weeks postpartum. Aim 3 Infant: infant growth (weight, length, and head circumference) from birth to 4 weeks.
Study Population:	Postpartum women who delivered an infant within the previous 7 days
Description of Sites	University of California, San Diego (UCSD)
Enrolling Participants:	
Study Duration:	1 year
Participant Duration:	8 weeks

## 2 INTRODUCTION

### 2.1 STUDY RATIONALE

Drospirenone-containing progestin-only pills (d-POPs) may be an acceptable alternative to Norethindrone-containing progestin-only pills (n-POPs) in the postpartum period when initiated either a week or month after delivery with fewer side effects and no impact on breastfeeding, breastmilk, and infant outcomes. Providing women with more options of safe, effective postpartum (PP) contraception has the potential to reduce unintended pregnancy and short inter-pregnancy intervals, thereby decreasing maternal and infant morbidity and mortality.

### 2.2 BACKGROUND

Use of postpartum (PP) contraception can help women achieve their reproductive goals and prevent short inter-pregnancy intervals (IPIs). Short IPIs (<18 months between birth and subsequent pregnancy) are associated with an increased risk of maternal and infant morbidity and mortality including preterm birth. One-third of pregnancies in the United States occur after short IPIs; and approximately 70% of pregnancies in the first year after delivery are unintended. Women who receive contraception after delivery are significantly less likely to have an unintended pregnancy and short IPI.

Contraception is typically initiated around 6 weeks after delivery; however, the timing is based on historical precedent, not evidence. By 6 weeks PP, more than half of women have resumed intercourse. The CDC provides guidance that it is difficult to be “reasonably certain that woman is not pregnant” beyond 4 weeks PP unless she meets the very stringent criteria for lactational amenorrhea (LAM) which includes exclusive breastfeeding and no interval of greater than 4-6 hours between feeds. Delaying access to PP contraception beyond 4 weeks may increase the risk of undesired pregnancy and short IPIs.

Breastfeeding has many important health benefits for both mothers and infants, as well as economic and environmental benefits for families and communities. The American Academy of Pediatrics recommends exclusive breastfeeding for the first 6 months of life. Many women want to understand the effects, if any, of contraceptives on breastfeeding outcomes. Among 1,308 pregnant and PP women, 79% reported that safety during breastfeeding was an “extremely important” consideration when choosing contraception.

The natural PP decline in serum progesterone triggers lactogenesis; therefore, there is theoretical concern that use of progestin-containing contraceptives within the first weeks after delivery could inhibit initiation of breastfeeding or impact establishment of supply or composition of breastmilk. In addition, since progestins have been detected in breastmilk, there is concern about the effect of progestin exposure on early infant growth and development. Most existing studies on PP use of progestins initiated within days of delivery are small and of poor to fair quality, but the available data suggest that there is no effect on onset of lactogenesis, quantity or composition of breastmilk, breastfeeding rates, or infant growth. However, the Centers for Disease Control and Prevention (CDC) Medical Eligibility Criteria (MEC) for contraceptive use cites a paucity of high-quality data for ongoing concerns about the potential effect of progestins on breastfeeding and infant growth and their decision to categorize progestins use in the early PP period as Category 2 (advantages generally outweigh theoretical or proven risks) instead of Category 1 (no restriction). Whether progestin use affects

breastfeeding performance or infant health was identified as a priority research gap by the CDC. High-quality data on the potential effects of the timing of progestin initiation on breastfeeding are urgently needed to inform national and international guidelines on contraceptive use during breastfeeding.

A new progestin-only pill containing drospirenone has benefits compared to traditional norethindrone progestin-only pills, including less reliance on a narrow window of time for pill intake to maintain efficacy, but data on use of this type of progestin in breastfeeding are lacking. Because estrogen-containing contraceptives are contraindicated for a minimum of 21 days PP due to the risk of thromboembolism, and have been associated with decreased breastmilk supply, progestin-only contraception, including progestin-only pills (POPs) are commonly used for contraception among breastfeeding women regardless of time since birth. Approximately 16-20% of PP women who intend to breastfeed choose POPs for contraception following delivery in the U.S, approximately 500,000 women per year.

Until recently, POPs containing 0.35 mg daily of the oral progestin Norethindrone (n-POPs) have been the only available POP (Table 1). Norethindrone is a variant of progestin derived from testosterone. N-POPs do not consistently inhibit ovulation; the contraceptive mechanism of action is primarily through progestin effects on the cervical mucous and endometrium. They require daily use with a narrow window of time for intake to maintain efficacy and are associated with unpredictable vaginal bleeding patterns and acne. Fewer than half of women who intend to use n-POPs PP use the method at 3 months. Women who choose n-POPs for PP contraception are significantly more likely to have a short IPI compared to women choosing all other reversible methods.

Drospirenone is a novel progestin derived from spironolactone (Table 1). POPs containing 4 mg of oral drospirenone (d-POPs) became available for use in the U.S. in 2019. D-POPs consistently suppress ovulation and allow for a wider missed-pill window and cyclic use with hormone-free days which offer the potential to improve ease of use and to decrease irregular bleeding. Unlike norethindrone, drospirenone has anti-androgenic properties and should not exacerbate acne and may improve it. The efficacy of d-POPs among non-breastfeeding women is similar to combined estrogen-progestin pills. However, little is known about the effect of d-POPs on breastfeeding performance or PP contraceptive use, efficacy, or side effects among PP women.

Table 1: Progestin types available as progestin-only pills for contraception in the United States

Progestin	Progestin Classification	Available in U.S.	Hormone-free days, 28-day cycle	Androgen effect	Metabolized into Ethinyl Estradiol
Norethindrone	19-nor testosterone, Estrane	1970	None	Medium-high	Small amount
Drospirenone	Spironolactone	2019	4	Antiandrogenic	None

D-POPs are promoted for use while breastfeeding despite a lack of data on the effect of d-POPs on breastfeeding or infant outcomes. The package insert states, “no effects on breastfed infants are

anticipated” but the only data presented to support the safety of d-POPs among breastfeeding women is an average drospirenone concentration in breastmilk over a 24-hour period of 5.6 ng/mL. Only 11 breastfeeding women were included in the published study on d-POP efficacy in the U.S. The single other published study evaluating d-POPs and breastfeeding outcomes was conducted among only 12 women and showed that 18.13% of plasma drospirenone was found in breastmilk. High quality data are required to inform CDC guidelines on use of differing progestin types during breastfeeding.

Most previous studies have failed to show a negative effect of progestins on breastfeeding or infant growth. However, most existing studies are small, are of poor to fair quality, do not include assessments of d-POPs users and do not use validated outcome measures. Furthermore, most studies evaluating the effect of POPs on breastfeeding have initiated the method at 6 weeks PP or later. The single study specifically evaluating the effect of early initiation of POBs was not randomized and compared all progestin users (including pills, injectables, and implants) to non-hormonal contraception users. That study did not show a deleterious effect of progestins on breastfeeding, but it was limited by lack of a comparison group allowing for assessment of differences in outcomes by progestin type or by timing of progestin initiation. Other randomized studies comparing the effect of early versus delayed initiation of progestins have evaluated different delivery systems such as intrauterine devices (IUDs) and implants. There are no studies comparing breastfeeding outcomes among d-POP and n-POP users. Most studies have examined the effect of progestins on maternal, milk, or infant outcomes in isolation and have failed to evaluate the effect of progestin exposure during breastfeeding on the mother-milk-infant triad. An adequately powered, high-quality, randomized controlled trial (RCT) using validated measures of maternal, infant and milk outcomes and including d-POP users is needed to minimize the effects of bias and confounding and overcome the weaknesses in the rigor of the prior research. Our goal with this pilot study is to inform a future large-scale randomized controlled trial.

## 2.3 RISK/BENEFIT ASSESSMENT

### 2.3.1 KNOWN POTENTIAL RISKS

1. There are potential risks of loss of confidentiality.
2. There is risk of stress, emotional distress, inconvenience, and possible loss of privacy associated with participating in a research study.
3. These are known risks of POBs, however they are routinely prescribed for women, both post-partum and otherwise.

### 2.3.2 KNOWN POTENTIAL BENEFITS

Patients may not experience a direct benefit from participation in this study. However, we hope that this study will help us determine if POBs can be provided during the early postpartum period with minimal impact on breastfeeding, infant growth and high patient satisfaction rates. There may be a benefit to women in the early initiation POP group to avoid unplanned early repeat pregnancies.

### 2.3.3 ASSESSMENT OF POTENTIAL RISKS AND BENEFITS

The potential benefit of early postpartum POP use outweighs the potential risks of changes to breastmilk, breastfeeding or infant growth changes.

## 3 OBJECTIVES AND ENDPOINTS

Aim	Variable	Description	Source
Maternal Outcomes			
1a	Breastfeeding	Exclusive breastfeeding : own mother's milk via breast or bottle. Predominant breastfeeding : greater than 75% of the infant's diet is their own mother's milk; the remainder of the diet is formula, donated milk, or other supplemental foods Mixed Breastfeeding : 25-75% or more of the infant's diet is their own mother's milk Predominantly supplementing : <25% diet is breastmilk No breastfeeding : infant is not consuming own mother's milk	End of weeks 2-8
1a	Supplementation type	Donated breastmilk, formula, other milks (cow, plant-based, nut), juice, water, cereal, other foods	End of weeks 2-8
1b	Progestin-only pill use	Any use, timing of initiation of POP use (assigned), type of POP (assigned), number of missed pills	End of weeks 2-8.
1b.	Contraception use	Sterilization (male and female), intrauterine devices, subdermal implants, oral contraceptives (combined), condoms (male and female), injectables, emergency contraceptive pills, patches, diaphragms, sponges, cervical caps, spermicidal agents, vaginal rings, withdrawal, fertility awareness, abstinence, and LAM	4 and 8 weeks
	Vaginal bleeding	Number of days of any bleeding and spotting in last month	Estimated at 4 and 8 weeks
	Satisfaction with contraception	Satisfied with method, would recommend method to a friend	4 and 8 weeks
	Pregnancy	Self-reported new pregnancy, pregnancy intendedness, whether planning to continue the pregnancy or not, and pregnancy outcome: continued, terminated, pregnancy loss	4 and 8 weeks
Milk Outcomes			
2	Composition of breastmilk	Fat, protein, carbohydrate (including oligosaccharide) content of milk	4-week breastmilk sample
	Maternal perception of adequate milk supply	Hill and Humenick Lactation Scale	End of weeks 2-8
Infant Outcomes			
3	Change in infant growth	Weight, length, and head circumference	Change between baseline and 4 weeks

## 4 STUDY DESIGN

### 4.1 OVERALL DESIGN

This is a three-arm, placebo-controlled, double-blinded randomized controlled pilot trial that includes 8 weeks of participation from enrollment to final follow-up.

We hypothesize that the type of progestin used and the timing of progestin initiation will not have clinically meaningful effects on breastfeeding continuation, supplementation, the composition of breastmilk, or infant growth and body composition. In addition, we hypothesize that the timing of progestin initiation will not have a meaningful effect on progestin-only pill (POP) continuation, but that women will be more likely to continue d-POPs compared to n-POPs. Findings from this study will support more women to use progestin-containing contraceptives to prevent unintended pregnancy in the postpartum period with a greater understanding of the safety while breastfeeding.

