## 9 STATISTICAL CONSIDERATIONS

### 9.1 STATISTICAL HYPOTHESES

Comparisons will be made between groups 1 and 2 to assess differences in outcomes by type of progestin used, and between groups 1 and 3 to assess differences in outcomes by timing of progestin initiation. The primary outcome is the proportion of women exclusively breastfeeding at 8 weeks postpartum. Differences in baseline demographic characteristics and in variables between groups will be assessed using  $\chi^2$ , Fisher exact, or t-tests as appropriate.

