## 9.2 SAMPLE SIZE DETERMINATION

The sample size (N=30 in 6 months) was chosen to demonstrate feasibility to enroll 180 women in 36 months at our site during a larger multi-site trial and to successfully complete follow-up.

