## 9.4 STATISTICAL ANALYSES

### 9.4.1 GENERAL APPROACH

### 9.4.2 ANALYSIS OF THE PRIMARY EFFICACY ENDPOINT(S)

A survival analysis will be conducted to to assess time spent exclusively breastfeeding.

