### 9.4.3 ANALYSIS OF THE SECONDARY ENDPOINT(S)

Proportions will be compared using chi-square tests. ANOVAs will be used to calculate means for analysis using all 3 groups and t-tests for any pairwise comparisons.

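### The no-meaningful-effect hypotheses in 4.1 are paired only with difference tests and an unspecified survival analysis, which do not address them; between-group estimates with intervals should be the main result

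*Combined protocol and SAP*

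**What the plan says.** Section 4.1 states two hypotheses in no-effect form. The first is that type and timing "will not have clinically meaningful effects on breastfeeding continuation, supplementation, the composition of breastmilk, or infant growth and body composition". The second is that the "timing of progestin initiation will not have a meaningful effect on progestin-only pill (POP) continuation". No size is attached to meaningful in either. The same paragraph names the expected use of the results: "support more women to use progestin-containing contraceptives to prevent unintended pregnancy in the postpartum period with a greater understanding of the safety while breastfeeding".

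The between-group analyses are these:

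- **9.1:** groups 1 v 2 for type and 1 v 3 for timing, with the proportion exclusively breastfeeding at 8 weeks as primary outcome. "Differences in baseline demographic characteristics and in variables between groups will be assessed using" chi-square, Fisher exact or t-tests.
- **9.4.1 (General Approach):** the heading has no text under it.
- **9.4.2:** "A survival analysis will be conducted to to assess time spent exclusively breastfeeding". No estimator, test, effect measure or interval is named.
- **9.4.3:** "Proportions will be compared using chi-square tests". For continuous outcomes the section gives this: "ANOVAs will be used to calculate means for analysis using all 3 groups and t-tests for any pairwise comparisons".

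On size, 9.2 says that N=30 "was chosen to demonstrate feasibility to enroll 180 women in 36 months at our site during a larger multi-site trial". Section 6.1 puts 10 women in each arm. Section 2.2 says that an adequately powered trial is needed and that this pilot is meant to inform it.

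**The concern.** A hypothesis of no clinically meaningful effect is informed by which effects the data rule out. A difference test asks only whether zero is implausible. Failing to reject zero does not show that large effects are implausible, and in a small sample it is the common outcome even when a large effect exists.

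Here a non-significant p-value would sit beside a hypothesis of no meaningful effect and an advance statement about supporting use during breastfeeding. The outcomes include exclusive breastfeeding and infant growth, where an overstated reassurance matters. For the pilot's declared purpose, the useful between-group result is the range of effects still open, and the plan does not make that range an output.

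The hypothesis that women are more likely to continue d-POPs than n-POPs is directional. A difference test suits it, and it is not part of this point.

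**Working it through.** **The plan's own figure.** Section 9.2: 30 women in 6 months is 30/6 = 5 per month; 180 in 36 months is 180/36 = 5 per month. The feasibility basis reproduces exactly. No alpha, power, effect size, margin, SD or expected rate is stated, so there is no power figure to reproduce.

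**Inputs.** n = 10 per arm (6.1). Comparisons 1 v 2 and 1 v 3 (9.1). Assumed here: 95% intervals and no losses.

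**Interval for a difference in proportions (Newcombe).** The Wilson limits for x/n are

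(p + z²/2n ± z√[p(1−p)/n + z²/4n²]) / (1 + z²/n), with z = 1.96.

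For 8/10 these are 0.490 and 0.943. For two arms that both observe 8/10, the half-width is

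√[(0.800 − 0.490)² + (0.943 − 0.800)²] = √(0.0960 + 0.0205) = 0.341.

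| Observed, 10 v 10 | Difference | 95% Newcombe interval |
|---|---|---|
| 5/10 v 5/10 | 0 | ±37 points |
| 7/10 v 7/10 | 0 | ±36 points |
| 8/10 v 8/10 | 0 | ±34 points |
| 9/10 v 9/10 | 0 | ±31.5 points |
| 10/10 v 10/10 | 0 | ±28 points |
| 5/10 v 8/10 | −30 | −60 to +11 points |

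The last row has p = 0.16 by uncorrected chi-square and p = 0.35 by Fisher. The p-value alone says not significant; the interval says that a 60-point fall has not been excluded.

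**Interval for a difference in means (milk composition, growth).** The half-width in SD units is t(0.975, 2n−2) × √(2/n). At n = 10: 2.101 × √0.2 = 0.94 SD. With 8 evaluable per arm: 2.145 × √0.25 = 1.07 SD.

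**How often the tests would be non-significant (illustration only).** Further assumptions: two-sided 0.05 and a reference exclusive-breastfeeding rate of 70% to 95% at 8 weeks. Fisher and chi-square figures are exact binomial enumeration. Log-rank, if that is what 9.4.2 intends, was simulated with a constant hazard over seven weekly reports.

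| True fall | Fisher | Uncorrected chi-square | Log-rank |
|---|---|---|---|
| 20 points | 94–95% | 86–87% | 84–85% |
| 30 points | 84–88% | 68–75% | 66–72% |

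At a 40-point fall the answer depends on the test and the reference rate (about 67–76% for Fisher, 47–58% for chi-square), so no general statement is made there. For means, a true 0.5 SD difference is missed about 81% of the time.

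**The case against.** The best case for the plan is that it never claims to establish absence of effect. It calls itself a pilot, rests N on enrolment feasibility, and says in 2.2 that an adequately powered trial is still needed. No significance threshold is stated, so every miss rate above rests on an assumed 0.05 and assumed rates, and a power argument against a trial that claims no power proves little. The intervals are also recoverable: group proportions and means will exist, anyone can compute a Newcombe interval from counts such as 8/10 v 8/10, and a survival analysis often yields curves and intervals.

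Much of this stands. The sample size is not at fault, the miss rates are only illustrative, and no information is lost for good. The blank 9.4.1 also calls for some caution, because text could have been lost from that section, although nothing marks a removal.

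A reader might infer that the plan intends to treat p > 0.05 as proof of no effect, that its outputs can never show what remains open, or that the trial is too small. The documents support none of these: no reading rule of any kind is given, the counts allow intervals afterwards, and feasibility is a proper basis for N=30.

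What the objection does not remove is the mismatch. The hypotheses are in no-effect form, the named between-group analyses test for a difference, and neither an interval nor a caution on interpretation is planned to connect the two.

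**Conclusion.** The point holds as a gap in estimation and interpretation, and should be fixed. The tests in 9.1 and 9.4.3 and the unspecified survival analysis in 9.4.2 do not address the no-effect hypotheses of 4.1. With 10 per arm and complete follow-up, even perfect agreement between arms leaves differences of about 28 to 37 points in a proportion, or 0.94 SD in a mean, compatible with the data at 95% confidence. Losses widen this.

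The interval widths need only n = 10 and the 95% level. The statement that the tests would usually be non-significant needs more: under the assumed two-sided 0.05 and reference rates of 70% to 95%, it holds for true falls of 20 to 30 points in exclusive breastfeeding and is not claimed beyond that.

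**What to change.** **(a) Make estimates the main result.** In 9.4.1 (now blank), 9.1 and 9.4.3, specify between-group estimates with 95% confidence intervals for 1 v 2 and 1 v 3:

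- exclusive breastfeeding at 8 weeks, the stated primary outcome: one risk difference with a small-sample interval, Newcombe or Miettinen–Nurminen, chosen in advance;
- supplementation and, for 1 v 3, pill use at 8 weeks: the same measure and method;
- milk composition at 4 weeks and change in growth from baseline to 4 weeks: mean differences.

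Keep the 9.4.2 survival analysis as supportive, with Kaplan–Meier curves. Do not add a Greenwood-based week-8 difference as a second main interval. With no losses it has the same point estimate as the risk difference, and in a 10/10 v 10/10 tie its standard error is zero, so the interval shrinks to a point where Newcombe gives ±28 points.

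**(b) Add a reading rule to 9.1.** For example: a non-significant difference will not be interpreted as absence of a clinically meaningful effect; estimates and confidence intervals will be used to plan the larger trial.

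Softening the sentence in 4.1 about supporting use is optional wording. No margin test is proposed, since even a 10/10 tie leaves ±28 points.

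**Cost.** Text changes only, with no extra participants, visits or data. The downside is a more modest claim and no yes/no answer on the no-effect hypotheses from the pilot.

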#### **Enrollment Procedures:**

We will assess women who indicate that they desire POPs for contraception for eligibility after they have received contraceptive counseling. Research staff will identify postpartum women who are planning on utilizing POPs as postpartum contraception via review of medical records of patients receiving inpatient obstetrical services at UCSD. Study staff will visit these potential participants during their inpatient hospital stay to present the study and administer the pre-screening eligibility form if the patient is interested in participation. While only women who intend to use POPs for at least 8 weeks will be enrolled, all participants will be told if they are unhappy with POPs at any time, the study team will facilitate timely contraceptive counseling and referral to an appropriate provider to ensure that they can switch contraceptive methods at any time if they choose.

After enrollment and prior to randomization, participants will be asked to complete a brief self-administered demographic questionnaire using a private secure tablet that enters data directly into REDCap (Research Electronic Data Capture), a secure electronic data collection system. Demographic characteristics collected will include maternal age, race, Body Mass Index, gestational weight gain, parity, education, previous experience breastfeeding, previous contraceptive use history, breastfeeding intentions, delivery type and complications, infant stay in neonatal intensive care unit (and length of stay), infant birth weight, race, sex assigned at birth, and gestational age at birth. Participants will receive a gift card via text or email link for completing the survey.

[figure not shown]

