**Figure 2: Outcome Evaluation Study Design**

**Surveys:**

Investigators will send participants hyperlinks via 5 text messages weekly at the end of weeks 2, 3, 5, 6, and 7 PP. Hyperlinks will lead to a brief questionnaire that participants can complete through a smartphone or tablet. Participants will complete a tablet-based survey in person at their 4 week visit. Participants will receive an emailed hyperlink at the end of week 8 which will lead to a longer questionnaire. A telephone survey will be available as an alternative to the digital questionnaires if desired. Survey questions will address continuation of and satisfaction with breastfeeding, the use of supplemental feeding, types of supplemental feeding being used, use of contraception, and satisfaction with contraception.

At 8 weeks PP, participants will be emailed and requested to complete a more detailed questionnaire eliciting breastfeeding continuation, supplementation amount and type, episodes of lactation support, perception of adequate milk supply, vaginal bleeding patterns, satisfaction with breastfeeding and

contraceptive use, satisfaction with contraception, infant health and well-being, and any new pregnancies and respective pregnancy outcomes if available. Additional potential confounding factors will be explored, such as use of nipple shields, pacifiers, breastmilk expression, and other medications the participant is using. Participants will receive a gift card via text or email link for each completed survey.

Both text and email questionnaires will be sent via a hyperlink that connects to a HIPAA-compliant secure platform that will input the data directly into a REDCap database. Participants who do not have smartphones or email access will be offered participation instead using phone surveys administered by study staff and gift cards will be mailed to these participants.

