#### **Breastmilk collection and analysis:**

Women will attend an in-person visit at 4 weeks PP with their infant. Participants will have the option to collect a mid-feeding sample at home with all pumping materials and instructions sent to her home or collect a sterile sample at the visit using a study-provided breast pump. 10 mLs of breastmilk from the collection (either refrigerated sample brought to the visit or collected on-site) will be frozen at the site of the visit at the research site. The milk samples will be frozen at -80 degrees onsite. The lab will use liquid chromatography to assess the composition of breast milk and compare the concentrations of total fat, total protein and carbohydrates including oligosaccharides.

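### Section 4.1 hypothesises no effect on infant body composition, but no aim, endpoint, procedure or analysis measures it, so that part cannot be tested

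*Combined protocol and SAP*

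**What the plan says.** The hypothesis in section 4.1 is one of no clinically meaningful effect, by progestin type or by timing of initiation. Its list of outcomes ends with "the composition of breastmilk, or infant growth and body composition".

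The operative text on infants is narrower:

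- Aim 3 in the synopsis (1.1) is "infant growth (weight, length, and head circumference) from birth to 4 weeks".
- The endpoint table (section 3) has one row under infant outcomes. It is labelled "Change in infant growth", described as "Weight, length, and head circumference" and timed as "Change between baseline and 4 weeks". No unit, growth standard or adjustment is named.
- At enrolment (8.1) the infant items include "infant birth weight, race, sex assigned at birth, and gestational age at birth".
- For the 4-week visit (8.1), "Women will attend an in-person visit at 4 weeks PP with their infant". The rest of that text concerns milk sampling.
- The 8-week questionnaire (8.1) asks the mother about "infant health and well-being, and any new pregnancies", among other topics.
- Section 9.4.3 gives chi-square tests, ANOVA and t-tests for secondary endpoints in general and names no infant variable.

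Two other provisions bear on timing. Section 5.1 admits women who delivered less than 168 hours earlier. Section 7.3 has a missed visit rescheduled within one week.

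**The concern.** The hypothesis asserts an absence of harm to infants, and section 4.1 goes on to expect that the findings will encourage wider use through better understanding of safety during breastfeeding. A component with no data should not sit under that statement. Section 2.2 says the pilot is meant to inform a larger trial, so an outcome that is hypothesised but never measured could be carried forward.

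A smaller, separate matter concerns the growth outcomes that are measured. Gains in grams and centimetres depend on the number of days elapsed and on infant sex. The plan fixes neither the scale of the change nor a single starting point, and the comparison has 10 infants per arm. Variation in age and sex would then add noise that has nothing to do with the pills.

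**Working it through.** **1. Trace the body-composition term through the plan.** No arithmetic applies; the sections are set side by side.

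| Place | Infant content | Body composition? |
|---|---|---|
| 4.1 hypothesis | Growth and body composition | Named |
| 1.1 Aim 3 | Weight, length, head circumference | No |
| 3 endpoint table | Change in the same three | No |
| 8.1 enrolment | Includes birth weight, sex, gestational age | No |
| 8.1 4-week visit | Infant attends; only milk collection described | No |
| 8.1 8-week questionnaire | Health and well-being | No |
| 9 analysis | No infant variable named | No |

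Every other use of the word composition refers to breastmilk. Aim 3 and the endpoint row agree with each other, so the outlier is section 4.1. Weight and length would allow a weight-for-length index, but none is planned, and it would be a proxy.

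**2. Elapsed time in the growth endpoint.** Inputs: follow-up to 4 weeks (1.1 and 3), enrolment limit of 168 hours (5.1), rescheduling within one week (7.3, read here as a visit up to 7 days late).

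- 4 weeks = 4 × 7 = 28 days; 168 hours = 168 / 24 = 7 days.
- Counted from birth: 28 days if on time, 28 + 7 = 35 days if a week late.
- Counted from an enrolment at the limit: 28 − 7 = 21 days if on time, 35 − 7 = 28 days if a week late.

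The interval behind a single change score can therefore lie anywhere from about 21 to 35 days. If baseline is taken to mean the birth measurements, the range is 28 to 35 days. The documents do not say which applies.

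**3. Effect of one late visit on an arm.** With 10 infants per arm (6.1), one infant seen 7 days late moves the arm's mean age at measurement by 7 / 10 = 0.7 days. Converting this to grams needs a daily gain that the documents do not give.

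**4. Precision in context.** Assume a two-sided 95% interval (the plan states no alpha) and all 20 infants in a pairwise comparison measured. The half-width for a difference in means is t(0.975, 18) × SD × √(1/10 + 1/10) = 2.101 × 0.447 × SD = 0.94 SD. A statement of no meaningful effect would be weak even for the growth measures that are collected.

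**The case against.** The strongest reply is that this is one stray phrase. The synopsis, the endpoint table and the risk-benefit statement (2.3.3) speak of infant growth only, the trial is a feasibility pilot (9.2), and its primary outcome is exclusive breastfeeding (9.1). That stands, and it keeps the point minor. It does not remove the mismatch, because section 4.1 is where the trial says what it expects to show.

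A reader might infer three stronger things that the documents do not support:

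- *That the trial will report a finding on body composition without data.* Section 4.1 states a hypothesis. No text commits the sponsor to such a finding.
- *That growth will be analysed in unadjusted grams and centimetres.* The endpoint table names no scale. What can be said is that the scale is unspecified.
- *That late visits will bias the growth comparison by a sizeable amount.* Allocation is randomised and blinded (6.2 and 8.1), so differing ages are noise unless attendance differs by arm, and nothing in the plan suggests that it does. No frequency of late visits is given, and any figure in grams would rest on an assumed daily gain.

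It is also fair to say that z-scores are a choice, since a randomised comparison of simple change is legitimate. Nor does an age- and sex-specific standard account for gestational age at birth, which may be any value from 37 weeks. Both points stand; the growth-scale advice is therefore offered as an improvement and not as the correction of an error.

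**Conclusion.** The body-composition part of the section 4.1 hypothesis has no aim, endpoint, procedure or analysis behind it and cannot be tested as planned. This rests on the text of the plan; Figure 2 was not available for the check, and a body-composition assessment shown there would still need an endpoint and an analysis. The consequence is limited to what the trial may claim about infants, and for 30 dyads it is minor.

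The secondary point is also modest. The start of the growth interval is described in two ways that can differ by up to 7 days, its end can move by up to a week on the reading of 7.3 used here, and the scale is not given. These add avoidable noise to a comparison that is already imprecise.

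**What to change.** 1. In section 4.1, delete the last three words of "the composition of breastmilk, or infant growth and body composition" and limit the infant hypothesis to growth in weight, length and head circumference. If a proxy is wanted, add weight-for-length at 4 weeks to the endpoint table and label it a proxy, not body composition.
2. Use the same starting point, birth or baseline, in Aim 3 and in the endpoint table, and apply it to every infant. Record the date of each measurement.
3. Analyse Aim 3 as change in z-scores from a published sex- and age-specific infant growth standard at exact age in days, shown beside grams and centimetres. The alternative is to adjust the change for infant sex and age at measurement.
4. Gestational age at birth, already collected at enrolment, can be added as a covariate, since step 3 does not correct for it.

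**Cost.** The hypothesis becomes narrower, and there is a short derivation step. The measurements are those Aim 3 already requires, but section 8.1 should say when and how the infant is measured: the enrolment list gives birth weight but not birth length or head circumference, and no infant measurement is described for the 4-week visit. With 20 infants per pairwise comparison, z-scores plus gestational age leave 20 − 3 = 17 residual degrees of freedom (intercept, arm, gestation). Covariate adjustment for sex, age and gestation leaves 20 − 5 = 15. This slightly favours the z-scores.
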